7.1 Primary Efficacy Endpoint

The primary efficacy endpoint is the proportion of subjects who are treatment failures during the double-blind randomized withdrawal period. After randomization, a treatment failure will be defined by the following criteria:

- 1. Any subject who experiences an increase of 20 mm or more above the baseline value on a 100 mm VASPI based on the average of 5 days, or
- 2. Any subject who experiences intolerable pain that in the opinion of the investigator requires intervention (i.e. rescue), or
- 3. Any subject who has other interventions for pain that violate the protocol from Day 84 to 119 that includes:
 - a. Requires oral opioid supplement in excess of 60 mg/day morphine-equivalent to manage withdrawal symptoms, or
 - b. Has a change in non-opioid oral prescription medications or nonpharmacological treatments being administered for the management of pain.

Note: A subject who does not have sufficient data for evaluation, drops out for any other reasons that are not listed above or who experiences withdrawal syndrome as identified by COWS > 12 during the double-blind treatment phase will **not** be classified as a treatment failure in the primary efficacy analysis.

VASPI Calculation Algorithm

VASPI scores will routinely be collected twice each day. The daily VASPI score from Day 77 to 119 will be computed as follows:

- As the average of the two scores when both of the twice-daily VASPI measures are present.
- If only one score is present, then the daily score will be equal to that non-missing value.

• If both scores are missing, then the daily score will be missing.

The 5-day baseline (Days 77-83) average VASPI will be computed as follows:

- If the daily score is present on days 79, 80, 81, 82, and 83, then the 5-day average is the average of days 79-83.
- If one of the daily scores from days 79-83 is missing, then the day 78 value (if present) will be included in the 5 daily scores to be averaged. If the day 78 value is also missing, then the day 77 value will instead be used.
- If two of the daily scores from days 79-83 are missing, then the day 78 and day 77 values (if present) will be included in the 5 daily scores to be averaged.

During the double-blind randomized withdrawal period, the 5-day average will be calculated as follows:

- If the daily score is present on all 5 consecutive days, then the 5-day average will be calculated using the data from these days.
- If any of the daily scores are missing, then the 5-day average will be based on the most recent 5 days for which daily scores are available.
- If 5 post-randomization daily scores are not available, then the average of the subject's available scores will be used.

In the event that a subject rescues for intolerable pain a self-initiated VASPI will be obtained, if possible. In this event, it is possible that more than one VASPI score may be obtained in the AM or PM time periods. In the event of more than one VASPI score recorded in the AM (12:01 am to 12:00 noon) or in the PM (12:01 noon to 12:00), the AM or PM values will be averaged to obtain a single AM or PM score for pain that will then be used in the algorithm above.

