Subjects may be given oral supplemental medication for pain up to a maximum of 180 mgequivalent morphine per day prior to Day 77 of treatment, however, the objective of the trial during this period is to achieve an optimal dose of intrathecal hydromorphone hydrochloride and reduce or eliminate any oral supplement. Oral supplement in excess of 180 mgequivalent morphine per day or other interventions due to intolerable pain, is not permitted and the subject will be withdrawn from the trial and weaned off intrathecal hydromorphone hydrochloride and converted to other appropriate pain therapies. From Day 77 to Day 119 or day of rescue, subjects are permitted up to 60 mg-equivalent morphine per day only to manage possible withdrawal symptoms.

On Day 77 the pump should be refilled with intrathecal hydromorphone and any final adjustments made to the daily dose or programming. On Day 77, the subject will be given a remote monitoring device to measure VASPI scores twice daily in the morning (5:30 am to 12:00 noon) and in the evening (6:00 pm to 11:45 pm). After Day 77 and during the randomized double-blind period there should be no dose adjustments to intrathecal hydromorphone hydrochloride other than those dictated by the protocol for subjects on the control arm who have their dose titrated downward. After Day 77, there should also be no changes to the pump programming for simple continuous, complex continuous or PTM dosing regimens until after the completion of the trial.

At the end of the 12 week continuous dosing period, subjects who meet criteria for randomization will be randomized in a 1:1 ratio to either remain at their current dose of hydromorphone or who have their dose titrated downward (control group) in a blinded fashion. The criteria for randomization is defined as an average VASPI score of 50 mm or less on a scale of 100 mm for the last 5 days with daily pain measurements prior to randomization on Day 84. After Day 77 the subject should be weaned off any oral supplement of opioid or other prescription medications prior to randomization. For those subjects randomized to be withdrawn from hydromorphone therapy on Day 84, the pump speed will be adjusted to decrease the total daily dose each 7 days (\pm 1 day), starting at a dose

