of 75%, 50%, 25%, 12.5% and approximately 0% of the dose at the time of randomization. For PTM dosing, the base continuous dose and the PTM dose would be decreased by the specified percentages above. The total maximum dose of 10 mg/day will be the combined total of the decreased base continuous dose and PTM dose. For those subjects randomized to stay on their current dose of hydromorphone hydrochloride, they will also return to the clinic on the same schedule for assessments and for mock pump adjustments. The blind will be maintained by having an independent unblinded medical professional at the site to manage the pump infusion rate and medication provided to the subject.

Pain assessments using the VASPI scale will continue twice daily (morning and evening) from Day 77 prior to the randomization period and throughout the randomized withdrawal period. COWS and SOWS assessments will be performed at specified time points to assess any withdrawal symptoms. Subjects will be permitted a maximum of 60 mg of morphine-equivalent oral opioid per day during the randomized withdrawal period only for the purpose of managing withdrawal symptoms. This oral supplement is not intended to manage pain and should be provided only if the subject starts to experience withdrawal symptoms. No other changes to prescription medications or non-pharmacologic interventions being used for pain are allowed from Days 84 to 119, or treatment failure.

Baseline pain for the double-blind randomized withdraw period is defined as the average of the last 5 days of the last 7 days with daily pain measurements while on the optimal intrathecal dose of hydromorphone hydrochloride, between Days 77 to 83 of the open-label dosing period.

After randomization, a treatment failure will be defined by the following criteria:

- 1. A subject who experiences an increase of 20 mm or more above the baseline value on a 100 mm VASPI based on the average of 5 days, or
- 2. A subject who experiences intolerable pain that in the opinion of the investigator requires intervention (i.e. rescue), or
- 3. A subject who has other interventions for pain that violate the protocol from Day 84 to 119 that includes:
 - a. Requires oral opioid supplement in excess of 60 mg/day morphine-equivalent to manage withdrawal symptoms, or
 - b. Has a change in oral prescription pain medications or non-pharmacologic treatments being administered to manage pain.

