Following the 5 week randomized withdrawal period, all randomized subjects may be allowed to continue on intrathecal hydromorphone hydrochloride for up to 12 months of safety evaluation by entering the open-label safety study (CNS-HYD202US). Subjects in the control group who had their dose titrated down will be first titrated back onto intrathecal hydromorphone hydrochloride as part of the CNS-HYD202US protocol. Subjects who do not experience adequate benefit or cannot tolerate intrathecal hydromorphone hydrochloride during the 12-week chronic dosing period will not enter the randomized withdrawal period of the trial, and thus not be eligible for the long term treatment protocol. Subjects who experience a drug related adverse event that requires discontinuation after randomization will also not be qualified for the long- term extension study, CNS-HYD202US. Subjects will be followed for safety for the duration of their treatment with intrathecal hydromorphone hydrochloride.

Table 1 and Table 2 contain the study schedule of assessments.

Study Procedure	Screening	Baseline	Titration			Visit Sc	hedule (Da	ys 1 to 56)		
Study Day ^a	Day ^b -14 to 1	Day ^c -3 to 1	Optional Days ^e	Day 1	Day 7	Day 14	Day 21	Day 28	Day 42	Day 56
Signed informed consent	Х									
Medical history	X									
Compete physical exam	Х									
Vital signs, Height and Weight	Х	X	Х	Х	Х	Х	Х	Х	Х	Х
Urine pregnancy test	Х	X								
$\mathrm{ECG}^{\mathrm{f}}$	X									
CBC, CMP, urinalysis ^g	X									
Concomitant medication assessment	X	Х		X	Х	Х	Х	Х	Х	X
Adverse event assessment	Х	X		Х	Х	Х	Х	Х	Х	Х
Hydromorphone HCl (Pump Refill)			X ^d	Xd						
Pump Dose Adjustment			Х	X						→
Oral Opioid (180 mg morphine-eq/day max.) ^h				X						→
Plasma concentration (PK) of Hydromorphone						Х				Х
Clinical evaluation for Inflammatory Granuloma ⁱ	X			Х	Х	Х	Х	Х	Х	Х
VASPI ^j	Х	Х	Х	Х	Х	Х	Х	Х	Х	Х
COWS ^k		Х	Х			Х				
SOWS ^k		Х	Х			Х				
SF-MPQ ^k		Х				Х		Х		Х
BPI ^k		Х				Х		Х		Х
PGIC ^k		X				Х		Х		Х

Table 1: Schedule of Study Procedures: Screening and Chronic Dosing Phase to Day 56

a. Study day is based on Day 1 defined as the first day at a therapeutic dose of intrathecal hydromorphone. There is no Day 0 in this trial. Visit days are ±2 day for Optional Titration Days and Days 1, 7, 14, 21, 28, 42 56 and 77. "Unscheduled Visits" will be considered as "Optional Days" for the purpose of study assessments.

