PGIC ^j		Х		Х		Х	Х	

Table 2: Schedule of Study Procedures: Final 7 Days of Continuous Dosing, Randomized Withdrawal and Efficacy Evaluation Period

a. Study day is based on Day 1 defined as the first day at a therapeutic dose of intrathecal hydromorphone., There is no Day 0 in this trial.

b. All visit days are +/- 1 day after Day 77 except for the final study visit.

c. On Days 84, 91, 98, 105 and 112 all subjects will have a pump adjustment. For those subjects randomized to maintain therapy, the adjustments will be a mock change to the dose, but no change will actually be made. For control group subjects randomized to be weaned off medication, the pump will be adjusted to give a 75%, 50%, 25%, 12.5% and 0% dose on each successive dose adjustment visit.

d. For the 0% dose, the pump will be set to the shipping mode (minimal speed possible)

e. On Day 119, or after treatment failure, all subject will receive scheduled Day 119 assessments before rescue medication is administered, if possible. If the subject cannot come to the site prior to rescue, they will be instructed to take a final VASPI using the remote monitoring device prior to taking oral rescue medication. After completion of the randomization period or rescue due to intolerable pain, subjects may be eligible to enter the CNS-HYD202US long term safety trial for an additional 12-months of hydromorphone therapy.

f. Subjects that discontinue or do not enter the CNS-HYD202US trial will return to the site 2 weeks after their last visit to have a final study visit. This visit can be +/- 4 days of the target date.

g. Oral opioid up to a maximum of 60 mg morphine-equivalence of oral opioid per day is allowed after Day 84 only for the purpose of managing withdrawal symptoms experienced as subjects are weaned off intrathecal medication. Doses of opioids in excess of 60 mg morphine-equivalence oral opioid per day, or other interventions to manage pain will be considered a treatment failure.

h. If there are clinical signs of an inflammatory granuloma as defined in Section3.3 (of the protocol), the Medical Monitor should be notified and an MRI or CT myelogram scheduled to confirm the pathology of the granuloma.

i. VASPI assessments are performed twice daily by the subject using a remote monitoring device that can capture VASPI measurements at approximately the same times each day.

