8.6 Comments on Statistical Analysis

The following general comments apply to all statistical analyses and data presentations:

Summaries will include frequency and percentages for categorical data and frequency, mean, standard deviation, median, minimum, and maximum for quantitative data.

- Where appropriate and unless otherwise specified, analyses will be presented by randomized treatment arm: hydromorphone arm or titrated down (control) arm.
- Duration variables will be calculated using the general formula: Duration = (end date start date) + 1.
- Individual subject listings of all data represented on the eCRFs will be provided to facilitate the investigation of tabulated values and to allow for the clinical review of all data.
- Version 9.1 or greater of SAS statistical software package will be used to provide all summaries, listings, and graphs described in this document.
- All raw data will be presented to the original number of data places. The means and medians will be presented to one more decimal place than the raw data. The standard deviations will be presented to two more decimal places than the raw data. For averages of averages, the means and medians will also be presented to one more decimal place than the raw data and the standard deviations will also be presented to two more decimal places than the raw data.
- Generally, the denominator for percentages will be based on the number of subjects in the study population. However, for cases where appropriate, the denominator for percentages will be based on the number of subjects with non-missing data appropriate for summary purposes. Unless otherwise noted, all percentages will be presented to one decimal place.
- There are approximately 10-30 study sites in this study. Due to the large number of study sites and the small numbers of subjects per site, the analysis of efficacy endpoints will not include adjustments for study site. However, descriptive summaries of the primary endpoint will be provided by site.

• Analyses for the randomization phase, Day 84 through Day 119, will be calculated for the period defined as randomization date through end of study date, as study day of randomization and Day 119 visit may not always occur on the scheduled study days (84 and 119) due to various circumstances.

9 Statistical Analyses

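### The SAP computes baseline VASPI from fixed study Days 79-83 with no cut-off at the actual randomization date, so the baseline of an off-schedule subject can contain post-randomization scores or differ from the qualifying mean.

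*SAP*

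**What the plan says.** SAP 7.1 (VASPI Calculation Algorithm) fixes the baseline days. Its first condition reads "If the daily score is present on days 79, 80, 81, 82, and 83", and in that case baseline is the mean of those five days. Day 78, and then Day 77, replace missing days. The rule does not mention the date or time of randomization.

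The footnotes to the SAP schedule tables fix what a day number means: "Study day is based on Day 1 defined as the first day at a therapeutic dose of intrathecal hydromorphone". They also give the tolerance around Day 84: "All visit days are +/- 1 day after Day 77 except for the final study visit".

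SAP 8.6 says that analyses of the randomized phase "will be calculated for the period defined as randomization date through end of study date". The reason given is that the randomization and Day 119 visits "may not always occur on the scheduled study days (84 and 119) due to various circumstances". SAP 10 lists this clarification under version 5.0 and lists no matching change to the baseline rule.

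Two statements in SAP 4 bear on the point. Baseline pain is measured on the optimal intrathecal dose, "between Days 77 to 83 of the open-label dosing period". Eligibility for randomization uses the average VASPI "for the last 5 days with daily pain measurements prior to randomization on Day 84". The protocol gives the same Day 77 to 83 range for baseline in the Synopsis and in Sections 3.1 and 3.5.1.3.

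**The concern.** Baseline is the reference for failure criterion 1 of the primary endpoint, a rise of 20 mm or more in the five-day average. The days that form this reference are counted from Day 1, while the phase compared with it starts at the actual randomization date. The two fit together only when randomization falls exactly on Day 84.

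With earlier randomization, the algorithm as written takes in scores from on or after randomization. In the control arm these can follow the first dose reduction. They would raise that arm's baseline and make a real 20 mm rise harder to reach. With later randomization, the algorithm ignores the most recent pre-randomization scores, so the reference value can differ from the mean on which the subject qualified at 50 mm or less.

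**Working it through.** **The plan's own figure.** SAP 8.1 states power above 90% for 40 per arm, 20% versus 55% failures and two-sided alpha 0.05. The pooled normal approximation gives 91.4%, and exact enumeration of the uncorrected Pearson test gives 91.5%. The stated power is reproduced, and nothing below changes it.

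**Day arithmetic.** Inputs are the baseline days 79-83 (SAP 7.1), study day counted from Day 1 and the ±1 day window (SAP schedule footnotes). Let R be the study day of actual randomization. A baseline day d is on or after randomization if d ≥ R. The five days just before randomization are R-5 to R-1.

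| R | SAP baseline days on or after R | Days R-5 to R-1 | Days shared with 79-83 |
|---|---|---|---|
| 83 (in window) | 83 | 78-82 | 4 |
| 84 (as scheduled) | none | 79-83 | 5 |
| 85 (in window) | none; Day 84 unused | 80-84 | 4 |
| 82 (outside) | 82, 83 | 77-81 | 3 |
| 88 (outside) | none | 83-87 | 1 |
| 91 (outside) | none | 86-90 | 0 |

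Within the window, at most one of the five baseline days is affected in either direction.

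**Size of the shift.** If one of five days is higher by D mm, baseline rises by D/5. The daily score is the mean of a morning and an evening reading. If only the evening reading follows the pump change, the daily score rises by D/2 and baseline by D/10. The rise needed for criterion 1, measured from the uncontaminated baseline, becomes 20 + D/5 or 20 + D/10. The documents give no D, so the values below are assumptions.

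| D (assumed) | Whole day affected: shift, effective threshold | Evening only: shift, effective threshold |
|---|---|---|
| 10 mm | 2 mm, 22 mm | 1 mm, 21 mm |
| 20 mm | 4 mm, 24 mm | 2 mm, 22 mm |
| 30 mm | 6 mm, 26 mm | 3 mm, 23 mm |

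The first control-arm step is to 75% of the dose, so a large D on the day of that step is not a natural expectation.

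**Scale on the endpoint.** One masked failure among 40 control subjects is 1/40 = 2.5 percentage points. If the expected control rate fell from 55% to 52.5%, planned power would fall from 91.4% to 87.1%. This shows what one reclassified subject is worth and does not estimate the effect. An estimate would need the day-to-day SD of VASPI, the size of D and the number of off-schedule subjects, and the documents give none of these.

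**The case against.** The strongest reply is that SAP 4 already excludes contaminated scores by definition, because a score taken after a dose reduction is neither open-label nor on the optimal dose. That stands as a statement of intent. However, SAP 7.1 is the rule that will be programmed, and for a subject randomized on Day 83 it returns a value that breaks the definition.

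The small in-window size also stands. One day in five is affected, after a step to 75% of the dose, and the morning reading may precede the pump change. Late randomization is milder still: at Day 85 four of five days are shared, and dose and programming are frozen after Day 77, so Days 79-83 remain a stable pre-randomization reference. Criteria 2 and 3 do not use baseline.

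Three stronger readings are tempting, and the documents do not support them.

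- A reader might take SAP 8.6 as evidence that randomization dates drifted widely. It says only that visits may not fall on schedule, which ±1 day shifts would satisfy. It sets no limit, but it does not report any out-of-window randomization.
- A reader might suppose that three or more baseline days could be contaminated. Randomization on Day 81 would leave only Days 77-80 on the device, one short of the five needed to qualify, unless the Day 77 visit was also early.
- A reader might say that the protocol's wording about scores before randomization makes a randomization-anchored baseline the protocol's own. That wording belongs to the eligibility criterion. The protocol's baseline definition names Days 77 to 83.

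**Conclusion.** The mismatch is real, and it affects the reference value for criterion 1 in subjects not randomized on Day 84. It can arise within the permitted visit window. There it involves at most one of five days: a shift of D/5, or about D/10 if only the evening score is affected. This conclusion takes the day numbers literally, counted from Day 1 as the schedule footnotes define them. If they were meant as the five days before the actual randomization visit, the problem would disappear, but the SAP does not say so.

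Contamination would raise baseline mainly in the control arm and mask failures there. It therefore works against showing superiority and does not point to a false positive. The late-randomization mismatch adds noise with no predictable direction. The effect on the failure rates cannot be quantified from the documents, because the number of affected subjects is not given. The mismatch itself is certain; its practical size is unknown and, within the window, probably small. The change should be made because the rule as written can give a wrong reference value and the repair is cheap.

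**What to change.** State in SAP 7.1 that no score taken after the actual randomization (or the first pump adjustment) enters baseline, and that the most recent earlier daily scores fill the gap. SAP 7.2.2 already uses the time of randomization, so the cut can be made by time. A Day 83 morning score taken before randomization would then count as that day's score under the existing single-score rule. State also what is done if fewer than five scores remain, because SAP 7.1 has no baseline rule for that case.

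In addition, run the primary analysis with baseline re-anchored to the five most recent daily scores on days R-7 to R-1, where R is the actual randomization day. List every subject whose baseline or failure status differs, and report both versions.

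The cost is SAP wording and a date condition in the program, with no new data. There is one small downside. SAP 2 says the study was already unblinded, and the protocol names Days 77-83. The change must therefore be labelled as made after unblinding and as a difference between SAP and protocol.

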7.2 Secondary Endpoints

Secondary endpoints include:

- The most important secondary endpoint is safety of intrathecal hydromorphone as assessed through collection of adverse events (AEs) and serious adverse events (SAEs) during the conduct of the trial. Particular attention will be paid to:
 - Rate of confirmed granulomas that are verified by MRI, CT Myelogram or by surgery.
 - Rate of possible granulomas

Other secondary endpoints include:

- Short-Form McGill Pain Questionnaire (SF-MPQ)
- Time to Rescue after Randomization
- Oral Opioid Supplement Consumption
- Brief Pain Inventory (BPI)
- Patient Global Impression of Change (PGIC)

